6.3.2. Analysis Methods for Exploratory Efficacy Endpoints

Time to first transplant will be summarized using descriptive statistics by treatment group for patients who are observed to initiate transplant in the ITT Analysis Set.

The duration of RBC transfusion independence will be analyzed in a similar manner as the analysis of DCR, as specified in Section 6.2.2.2. The censoring rule for duration of RBC transfusion independence is summarized in Table 6-1.

The transplantation rate will be analyzed in a similar manner as the analysis of ORR, as specified in Section 6.2.2.1.

A by-subject listing for RBC transfusions required throughout the study will be provided by treatment group and subject ID in chronological order. Date of transfusion, transfusion type, and the number of units transfused will be presented.

6.4. Patient-Reported Outcome

6.4.1. Definition of Patient-Reported Outcome Data

Four PRO instruments will be administered in this study: the Functional Assessment of Cancer Therapy-Anemia (FACT-Anemia), the 5-level EuroQol 5 dimensions (EQ-5D-5L), the Patient Global Impression of Severity (PGIS), and the Patient Global Impression of Change (PGIC).

Functional Assessment of Cancer Therapy-Anemia is described in Section 6.2.1.

The EQ-5D-5L is an instrument for use as a measure of health outcome and consists of 2 sections: the EQ-5D descriptive system and the EQ visual analogue scale (EQ VAS). The questionnaire is provided in the protocol Appendix D.

The EQ-5D descriptive system comprises 5 dimensions: mobility, self-care, usual activities, pain/discomfort, and anxiety/depression. Each dimension has 5 levels: no problems, slight problems, moderate problems, severe problems, and extreme problems. The patient is asked to indicate his/her health state by ticking the box next to the most appropriate statement in each of the 5 dimensions. This decision results in a 1-digit number that expresses the level selected for

that dimension. The digits for the 5 dimensions can be combined into a 5-digit number that describes the patient's health state. The VAS records the subject's self-rated health on a vertical VAS in which the endpoints are labeled "best imaginable health state" on the top and "worst imaginable health state" on the bottom. Higher EQ VAS indicates better health.

The PGIS and PGIC assessments are both single-item assessments used to demonstrate sensitivity and meaningful change thresholds and bolster the validity of selected PRO assessments for health-related quality of life and the physical function. The questionnaires are provided in the protocol Appendix E.

6.4.2. Analysis of Patient-Reported Outcome Data

In addition to the analyses specified in Section 6.2 for the secondary PRO endpoint, exploratory analyses comparing the effects of magrolimab + azacitidine versus placebo + azacitidine on health-related quality of life will be performed on the 4 PRO measures: FACT-Anemia, EQ-5D-5L, PGIS, and the PGIC. Analyses will be based on the ITT Analysis Set.

FACT-Anemia

- FACT-G: Mean total score and subscale scores at baseline and all follow-up timepoints will be summarized by treatment arm. The FACT-G consisits of the physical, social/family, emotional, functional subscales.
- FACT TOI-An: Mean total score and subscale scores at baseline and all follow-up timepoints will be summarized by treatment arm. The FACT TOI-An consists of the physical, functional and anemia symptoms subscales.
- FACT TOI-F: Mean total score and subscale scores at baseline and all follow-up timepoints will be summarized by treatment arm. The FACT TOI-F consists of the physical, functional and fatigue subscales.
- FACT-F: Mean total score and subscale scores at baseline and all follow-up timepoints will be summarized by treatment arm. The FACT-F consisits of the physical, social/family, emotional, functional and fatigue subscales.

EQ-5D-5L

The EQ-5D-5L data will be summarized by treatment group and visit as the following:

- A health profile: summary statistics will be provided, including number and percentage of patients who report each response category for the 5 dimensions (mobility, self-care, usual activity, pain/discomfort, and anxiety/depression).
- A self-perceived current health score: calculated from patient level EQ VAS responses (continuous variable). Descriptive statistics will be provided.

PGIC/PGIS

The proportion of patients who report each response category on the PGIC and PGIS at scheduled time-point will be summarized by treatment group. Descriptive statistics will be calculated for PGIC and PGIS at scheduled time-point. The mean and change from baseline on the PGIS to each subsequent assessment may be summarized.

Additional exploratory analyses may be conducted and documented in a separate PRO SAP.

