- f Response assessment at EOT visit not required if performed within the last 30 days or progressive disease has been documented. After disease progression (including treatment failure by IWG criteria and relapse after CR or PR), response assessment will focus on evaluation of transformation to AML.
- g Paper PROs will be administered in this study: The FACT-Anemia questionnaire, the EQ-5D-5L, the PGIS, and the PGIC will be administered. The participant should complete these questionnaires before other study procedures at required visits. FACT-Anemia and EQ-5D-5L should be implemented prior to PGIS/PGIC. FACT-Anemia, EQ-5D-5L, the PGIS, and the PGIC should also be collected during long-term follow-up prior to initiation disease progression or initiation of a new anticancer therapy.
- h Report all AEs through the Safety Follow-up Visit/Call and any treatment-related SAEs thereafter.
- i Collect blood transfusions until start of new anticancer therapy.
- j Collect new anticancer therapy data following the last dose of study treatment.
- k For participants who do not initiate new anticancer therapy after the last dose. See Section [5.1.10](#) for adverse event reporting details.

Table 6. Schedule of Assessments - Repriming (Required After > 4 Weeks Have Lapsed Since the Last Dose of Magrolimab/Placebo Delays)

Visit Window (Days)	Day										
	1	2	3	4	5	6	7	8	11	15	22
	-	-	± 3	± 3	± 3	± 3	± 3	± 3	± 3	± 3	± 3
Pregnancy test	X										
CBC with differential, platelets, and reticulocytes ^{a,b}	X	X		X				X	X	X	X
Haptoglobin and LDH	X							X			
Serum or plasma chemistry ^a	X							X		X	X
Peripheral smear ^{a,c}	X	X							X		
Peripheral blood for biomarker studies ^d	X							X			
PK ^d	X							X			
Antidrug antibodies ^a	X										
Vital signs ^c	X	X						X		X	X
Symptom-directed physical examination ^a	X							X		X	
Adverse events	X	X	X	X	X	X	X	X	X	X	X
Concomitant medications	X	X	X	X	X	X	X	X	X	X	X
Blood transfusions	X	X	X	X	X	X	X	X	X	X	X
Premedication ^f	X			X				X	X		
Magrolimab/placebo: repriming ^g	X			X				X	X	X	X

Abbreviations: CBC = complete blood count; ECOG = Eastern Cooperative Oncology Group; LDH = lactate dehydrogenase; PK = pharmacokinetic(s); PRO = patient-reported outcome; WBC = white blood cell.

a Pretreatment assessments are to be collected within 24 hours prior to study treatment administration.

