8.7. Analysis of PRO Data

A key PRO endpoint, FACT-Anemia response rate, is defined based on the ITT Analysis Set (see Section 8.3.1). The analysis method is similar to that of the CR rate. Other indices, such as the Functional Assessment of Cancer Therapy-General (FACT-G), FACT Trial Outcome Index-Anemia scale (FACT TOI-An), and FACT Trial Outcome Index-Fatigue (FACT TOI-F), which can be derived from FACT-Anemia with published minimally clinically meaningful difference, will also be analyzed {[Cella 2002](#), [Revicki 2013](#)}.

Additional analyses will be conducted on all PRO data, including absolute scores and changes from baseline for all items and subscales of the FACT-Anemia instrument, EQ-5D-5L instrument, and PGIS/PGIC at each assessment time point for each arm.

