- To evaluate RBC transfusion independence of magrolimab + azacitidine compared with that of azacitidine + placebo among all patients irrespective of RBC transfusion-dependence at baseline
- To evaluate the HRQoL of magrolimab + azacitidine compared with that of azacitidine + placebo, as measured by score change from baseline in FACT-Anemia, Patient Global Impression of Severity/Patient Global Impression of Change (PGIS/PGIC), and 5-level EuroQol 5 dimensions (EQ-5D-5L) questionnaires
- To assess biomarkers including but not limited to, immune cell recruitment, immune cell signaling, and bone marrow penetration of magrolimab

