3.6. Missing Data and Outliers

3.6.1. Missing Data

In general, missing data will not be imputed unless methods for handling missing data are specified. Exceptions are presented in this document.

The handling of missing or incomplete dates for disease diagnosis is described in Section 5.3, for the death date and the start date of new anticancer therapy in Section 6.1.1, for AE onset in Section 7.1.5.2, and for prior and concomitant medications in Section 7.4.

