9. PHARMACODYNAMIC ANALYSES

Exploratory analyses may be performed to evaluate the association of each biomarker or combination of biomarkers with clinical outcomes. Additional details will be provided separately by the biomarker sciences group.

10. Changes From Protocol-Specified Analyses

There are no deviations from the protocol-specified analyses.

11. **REFERENCES**

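### SAP 6.4.2 leaves out the change-from-baseline analyses of the exploratory PRO scores that protocol 8.7 commits to and SAP 1.1 names as the objective, and SAP Section 10 does not declare the omission

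*SAP*

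**What the plan says.** Protocol 8.7 states that further analyses of all PRO data will be done at each assessment time point for each arm, "including absolute scores and changes from baseline for all items and subscales of the FACT-Anemia instrument, EQ-5D-5L instrument, and PGIS/PGIC". SAP 1.1 lists an exploratory objective that compares quality of life between the arms "as measured by score change from baseline in FACT-Anemia", PGIS/PGIC and EQ-5D-5L.

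SAP 6.4.2 announces exploratory comparisons of the two arms on the four PRO instruments, then specifies:

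- **FACT-G, TOI-An, TOI-F and FACT-F:** "Mean total score and subscale scores at baseline and all follow-up timepoints will be summarized by treatment arm".
- **EQ-5D-5L:** "The EQ-5D-5L data will be summarized by treatment group and visit as the following", followed by response-category counts for the five dimensions and descriptive statistics for the VAS.
- **PGIS and PGIC:** response-category proportions and descriptive statistics at scheduled time points, and for the PGIS alone, "The mean and change from baseline on the PGIS to each subsequent assessment may be summarized".

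It closes by allowing that additional exploratory analyses may go into a separate PRO SAP. On missing data, SAP 3.6.1 says: "In general, missing data will not be imputed unless methods for handling missing data are specified". Section 6.4.2 specifies no such method. SAP Section 10 says: "There are no deviations from the protocol-specified analyses".

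**The concern.** The protocol promises an analysis, the SAP names it as the measure for an objective, and the section that should deliver it does not. A programmer working from SAP 6.4.2 would produce no change-from-baseline table for any FACT score or for the EQ VAS. A reader relying on Section 10 would not learn that anything had been dropped.

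The choice of summary also matters. A visit mean is taken over the participants who still complete forms at that visit. Under protocol Table 5, PRO forms in long-term follow-up "should also be collected during long-term follow-up prior to initiation disease progression or initiation of a new anticancer therapy", so loss of PRO data is tied to disease course. If those lost had worse scores from the start, the visit mean rises although nobody improves. If loss differs between arms, part of any difference in means reflects who is left.

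**Working it through.** **Text check.**

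| Instrument | Protocol 8.7 and SAP 1.1 | SAP 6.4.2 |
|---|---|---|
| FACT scores | change from baseline | visit means only; FACT-Anemia total not listed |
| EQ-5D-5L | change from baseline | category counts, descriptive VAS |
| PGIS | change from baseline | proportions and descriptive statistics; change only as *may* |
| PGIC | named with PGIS | proportions and descriptive statistics |

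The PGIC row is not a real gap. Protocol Table 3, footnote a, excludes the PGIC at Cycle 1 Day 1, so it has no baseline and is itself a rating of change.

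The other rows cannot be read as shorthand. Where the SAP wants change from baseline it says so: SAP 7.2.1 lists change at every postbaseline visit for laboratory tests, and SAP 7.3 lists change to the postbaseline maximum and minimum for weight and vital signs.

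**Size of the completer effect.** The documents state no PRO standard deviation, dropout rate or power, so there is no figure to reproduce. Assumptions for illustration:

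- f = fraction of an arm no longer observed at the visit, 20% to 50%
- d = how far the baseline mean of those lost lies below that of the stayers, 5 to 10 points, the same in both arms
- no participant's score truly changes

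Let m be the stayers' mean. The whole arm's baseline mean is (1 − f)·m + f·(m − d) = m − f·d, and the visit mean is m. The visit mean therefore rises by f·d:

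- smallest: 0.2 × 5 = 1.0 point
- largest: 0.5 × 10 = 5.0 points

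The false gap between arms is (f_exp − f_ctl)·d:

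- equal loss, 30% and 30%: 0
- 40% and 20%: 0.2 × 5 = 1.0 to 0.2 × 10 = 2.0
- 50% and 20%: 0.3 × 5 = 1.5 to 0.3 × 10 = 3.0

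Paired change from baseline in the same observed participants is 0 in every case.

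**Limit of the remedy.** Suppose those lost worsen by w = 5 to 10 points without this being observed, and 20% to 40% are lost. The true mean change is −f·w, from −0.2 × 5 = −1.0 to −0.4 × 10 = −4.0, while the observed change is still 0.

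**Precision.** Baseline adjustment cuts the variance of the comparison of follow-up scores by rho squared: 25% at rho = 0.5 and 49% at rho = 0.7 (assumed correlations).

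**The case against.** The best defence is that quality of life is already handled where it counts. SAP 6.2.1 defines the key secondary FACT-Anemia response rate with a 7.0-point improvement cutoff and counts participants without baseline or postbaseline forms as non-responders. SAP 6.2.2.1 analyses it like CR rate, and SAP 2.1 puts it in the testing hierarchy. SAP 6.4.2 is expressly additional to that. This stands: a reader might infer that the trial's quality-of-life objective as a whole goes unanswered, and the documents do not support that.

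Three further points have some force:

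- Protocol 8.7 asks for summaries by arm and does not require a model. True, but SAP 6.4.2 announces a comparison of the arms and gives no method, so a method has to be named.
- A separate PRO SAP may contain these analyses. It is optional, is described as covering additional work, and is not among the documents. The omission is established for this SAP only, but an optional document does not discharge a protocol commitment.
- The five FACT-Anemia subscales all appear in 6.4.2 through FACT-G and TOI-An. Correct, but only as visit means.

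The illustration also has limits. A reader might set the 1.0 to 5.0 point drift within an arm against the SAP's 7.0. That cutoff classifies improvement in an individual participant and is no yardstick for a shift in an arm mean. What could mislead is the gap between arms, which is zero with equal loss and a common d.

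**Conclusion.** The mismatch is established from the text and needs no assumption: changes from baseline are promised in protocol 8.7, define the exploratory objective in SAP 1.1, are missing or optional in SAP 6.4.2, and are not declared in Section 10. The consequence is confined to exploratory, untested PRO endpoints. No alpha and no primary or key secondary conclusion is touched.

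The possible distortion, a false arm gap of 0 to 3.0 points, rests wholly on assumed loss of 20% to 50% and an assumed baseline gap of 5 to 10 points common to both arms. It shows how visit means can mislead and is not an estimate for this trial.

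A reader might also infer that change from baseline would cure the dropout problem. It removes the shift caused by a changing mix of baseline scores. It does not remove bias from participants who worsen unobserved and leave.

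**What to change.** In SAP 6.4.2:

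1. Add change from baseline by visit and arm, with the number of participants observed at each visit, for the FACT-Anemia total and subscales, FACT-G, TOI-An, TOI-F, FACT-F, EQ VAS and PGIS. Leave PGIC as planned. Keep the visit means as supporting tables.
2. For the arm comparison, specify a repeated-measures model with baseline score, visit, arm, arm by visit and the stratification factors. State that it does not remove bias from loss caused by unobserved worsening.
3. If the sponsor chooses not to do this, list the omission in Section 10. The same applies to the item-level changes and EQ-5D-5L dimension changes that protocol 8.7 also covers, if they are not produced. Under SAP Section 1, a change made after the SAP is final goes in the clinical study report.

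The cost is SAP wording and some additional PRO tables. The forms are already scheduled on Day 1 of each cycle (protocol Table 3), and SAP Table 3-2 already defines the baseline and visit windows.

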7. SAFETY ANALYSES

7.1. Adverse Events and Deaths

7.1.1. Adverse Event Dictionary

Clinical and laboratory adverse events (AEs) will be coded using the current version of MedDRA. System organ class (SOC), high-level group term (HLGT), high-level term (HLT), preferred term (PT), and lower-level term (LLT) will be provided in the AE dataset.

7.1.2. Adverse Event Severity

Adverse events are graded by the investigator as Grade 1, 2, 3, 4, or 5 according to CTCAE Version 5.0. The severity grade of events for which the investigator did not record severity will be categorized as "missing" for tabular summaries and data listings. The missing category will be listed last in summary presentation.

7.1.3. Relationship of Adverse Events to Study Drug

Related AEs are those for which the investigator selected "Related" for a drug on the AE CRF to the question of "Related to Study Treatment." Relatedness will always default to the investigator's choice, not that of the medical monitor. Events for which the investigator did not record relationship to study drug will be considered related to study drug for summary purposes. However, by-subject data listings will show the relationship as missing.

7.1.4. Serious Adverse Events

Serious adverse events (SAEs) will be identified and reported as SAEs if the AEs met the definitions of SAEs that were specified in the study protocol. Serious adverse events captured and stored in the clinical database will be reconciled with the SAE database from the Gilead Global Patient Safety before data finalization.

7.1.5. Treatment-Emergent Adverse Events

7.1.5.1. Definition of Treatment-Emergent Adverse Events

Treatment-emergent adverse events (TEAEs) are defined as any AEs with an onset date on or after the study drug start date and no later than 70 days after the study drug last dose date or the day before initiation of new anticancer therapy including SCT (whichever is earlier). If the AE onset date is on or before the last dose date, the AE is considered as TEAE regardless of the start of new anticancer therapy.

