5.1.10. Adverse Events

At each visit, the following AEs are to be reported using the applicable electronic case report form (eCRF; Section [10.2.3.1](#)):

- After informed consent, but prior to initiation of study treatment, all AEs related to protocol-mandated procedures.
- After the first dose of study treatment, all AEs observed by the Investigator or reported by the participant that occur through 30 days after last dose of study treatment. Adverse events occurring after 30 days of last dose of study treatment will be reported until either 70 days after the last dose or until the initiation of new anticancer therapy (including SCT), whichever is earlier.

Details of adverse event reporting can be found in Section [7.2](#).

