7.7.2. Adverse Events

Following initiation of study medication, all AEs, regardless of cause or relationship, will be collected until 30 days after last administration of study drug and reported on the eCRFs as instructed. Adverse events occurring more than 30 days after the last dose of study drug will be reported until 70 days after the last dose of study drug or until the initiation of new anticancer therapy (including SCT), whichever is earlier.

All AEs should be followed up until resolution or until the AE is stable, if possible. Gilead may request that certain AEs be followed beyond the protocol-defined follow-up period.

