8.6. Safety Analysis

The statistical analysis of safety data will be conducted in the Safety Analysis Set. Safety variables may include, but are not limited to, treatment-emergent adverse events (TEAEs; AEs occurring during or after a participant's first exposure to study treatment and up to 70 days after the last day of study treatment or initiation of new anticancer therapy, including SCT [whichever is earlier]), vital signs, physical examinations, and laboratory tests.

Data may be graphed, summarized, or listed, depending on the amount of data to be reported.

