7.1.6.1. Summaries of AE incidence in Combined Severity Grade Subsets

A brief, high-level summary of the number and percentage of patients who experienced at least 1 TEAE in the categories described below will be provided by treatment group.

The number and percentage of patients who experienced at least 1 TEAE will be provided and summarized by SOC, PT, and treatment group.

- TEAEs
- TEAEs with Grade 3 or higher
- TE treatment-related AEs for any study drug and for each study drug
- TE treatment-related AEs with Grade 3 or higher for any study drug and for each study drug
- TE SAEs
- TE treatment-related SAEs for any study drug and for each study drug
- TEAEs leading to dose reduction of azacitidine
- TEAEs leading to discontinuation of any study drug and for each study drug
- TEAEs leading to death

Multiple events will be counted only once per subject in each summary. Adverse events will be summarized and listed first in alphabetic order of SOC and then by PT in descending order of frequencies in magrolimab + azacitidine treatment arm within each SOC. For summaries by severity, the most severe grade will be used for those AEs that occurred more than once in a given subject during the study.

In addition to the above summary tables, all TEAEs, TEAEs of Grade 3 or higher, TE SAEs and TEAEs leading to death will be summarized by PT only in descending order of frequencies in magrolimab + azacitidine treatment arm.

In addition, data listings will be provided for the following:

- All AEs, indicating whether the event is treatment emergent
- All SAEs
- All Deaths
- All SAEs leading to death
- All AEs with severity of Grade 3 or higher
- All AEs leading to discontinuation of study drug
- All AEs leading to dose reduction of azacitidine
- TEAEs leading to dose delay or interruption of study drug

A summary (number and percentage of patients) of deaths will be provided by treatment group. Summary will include the following categories:

- All deaths
- Deaths within 30 days of the first dosing of study drug
- Deaths within 30 days of the last dosing of study drug
- Deaths within 60 days of the first dosing of study drug
- Deaths within 70 days of the last dosing of study drug
- Deaths beyond 30 days of the last dosing of study drug
- Deaths beyond 70 days of the last dosing of study drug

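### AEs that start after new anticancer therapy but within 30 days of the last dose are collected yet missing from every by-arm AE table; a supplementary by-arm set would restore them

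*SAP*

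**What the plan says.** **Collection.** After the first dose, Protocol 5.1.10 requires reporting of "all AEs observed by the Investigator or reported by the participant that occur through 30 days after last dose of study treatment". Protocol 7.7.2 repeats this: "all AEs, regardless of cause or relationship, will be collected until 30 days after last administration of study drug". New therapy matters only for later events, which are reported "until 70 days after the last dose of study drug or until the initiation of new anticancer therapy (including SCT), whichever is earlier". The visit schedule agrees. In Protocol Table 5 the restriction "For participants who do not initiate new anticancer therapy after the last dose" is attached to the 70-day safety contact and not to the 30-day one, and Protocol 5.7.1 makes the 30-day call unconditional.

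**Analysis.** SAP 7.1.5.1 closes the TEAE window "no later than 70 days after the study drug last dose date or the day before initiation of new anticancer therapy including SCT", and the first of these two dates applies. SAP 7.1.5.2 applies the same limit to incomplete onset dates. The only protection is for onset on or before the last dose date, where "the AE is considered as TEAE regardless of the start of new anticancer therapy". Nothing similar covers Days 1 to 30 after the last dose. Protocol 8.6 also ends the window at new therapy, so the two documents agree on the analysis definition.

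**Reporting.** The by-arm AE tables in SAP 7.1.6.1 and the special-interest tables in 7.1.7.1 are built on TEAEs. Events that are not treatment-emergent go to listings (Protocol 8.6.2, SAP 7.1.6.1). Deaths have their own by-arm summary in SAP 7.1.6.1, with rows such as "Deaths within 30 days of the last dosing of study drug" that are not cut at new therapy.

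**The concern.** The protocol treats the first 30 days after the last dose as a period in which every AE matters, whatever treatment follows. The TEAE definition does not. A participant who stops study treatment and starts another therapy a week later has AEs recorded for 30 days but counted for six.

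The loss need not be equal in the two arms. Starting new therapy depends on response, progression and transformation, which the experimental treatment is meant to change. Early post-dose toxicity could therefore be undercounted more in one arm than in the other, in either direction, and the by-arm tables alone would not show it. What is at stake is the term, grade and relatedness of early post-dose events, fatal ones included. Survival data are not affected.

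**Working it through.** The plan states no figure on this point, so there is none to reproduce. The check compares the two windows day by day.

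**Inputs.** Let k be the onset day after the last dose and d the day on which new therapy starts.

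- Collected (Protocol 5.1.10, 7.7.2): k ≤ 30 for any d; or k from 31 to 70 with k < d.
- Treatment-emergent (SAP 7.1.5.1): k ≤ min(70, d - 1).
- Arm size (Protocol 8.1): 520 / 2 = 260.

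**Step 1: the gap.** For d from 1 to 30, collected days minus TEAE days = 30 - (d - 1) = 31 - d. For d ≥ 31 the two windows coincide.

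| New therapy starts on Day d | Days collected | Days counted as TEAE | Gap |
|---|---|---|---|
| 1 | 30 | 0 | 30 |
| 7 | 30 | 6 | 24 |
| 14 | 30 | 13 | 17 |
| 21 | 30 | 20 | 10 |
| 28 | 30 | 27 | 3 |
| 30 | 30 | 29 | 1 |
| 31 | 30 | 30 | 0 |

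**Step 2: one case.** New therapy starts on Day 10 and pneumonitis on Day 12. It is collected, since 12 ≤ 30. It is not treatment-emergent, since 12 > 10 - 1 = 9. It therefore appears in the listings but not in the TEAE or special-interest tables. If it is fatal by Day 30, the death enters the 30-day death row, but the AE does not enter the table of fatal TEAEs.

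**Step 3: transplant.** Protocol 5.7.1 recommends a 4-week magrolimab washout before conditioning. If that is followed and magrolimab was the last study drug given, d is about 28 or 29 and the gap is 3 or 2 days. The washout is a recommendation and does not name azacitidine, so the gap can be longer. Even so, most of the exposure lies with participants who start non-transplant therapy early.

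**Step 4: scale, under assumptions.** The documents give no rate or timing of switching. Assume that a share p of participants who stop treatment start new therapy uniformly over Days 1 to 30. The mean of 31 - d is then (30 + 29 + ... + 1) / 30 = 465 / 30 = 15.5 days, so the mean loss per participant is 15.5p days. For the share of all observation, take six 28-day cycles plus 30 days: 168 + 30 = 198 days.

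| p (assumed) | Participants of 260, if all have stopped | Mean days lost | Share of the 30 post-dose days | Share of 198 days |
|---|---|---|---|---|
| 5% | 13 | 0.8 | 2.6% | 0.4% |
| 20% | 52 | 3.1 | 10.3% | 1.6% |
| 40% | 104 | 6.2 | 20.7% | 3.1% |
| 60% | 156 | 9.3 | 31.0% | 4.7% |

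If p were 20% in one arm and 40% in the other, the mean loss would be 3.1 against 6.2 days. These are shares of observation time, not of events.

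**Step 5: with the collection window.** If the analysis window is onset through Day 30 for any d, plus Days 31 to 70 before new therapy, the gap is 0 for every d.

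**The case against.** The strongest reply is that the plan contains no error. Protocol 8.6 prespecifies the cut, the SAP implements it, and a sponsor may collect more than it tabulates. Ending the window at new therapy also has a purpose: it keeps salvage or conditioning toxicity out of tables meant to describe the randomized drugs. Moving the primary cut would let that toxicity in, and if switching differs by arm, so would the contamination. This stands, and it is why the primary definition should not be replaced.

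Several stronger readings are tempting, but the documents do not support them.

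- *Fatal outcomes are left out of the comparison.* They are not. SAP 7.1.6.1 tabulates all deaths by arm, and deaths within and beyond 30 and 70 days of the last dose, without a cut at new therapy. Every death is also an OS event. Only the AE detail is lost.
- *The death and fatal-TEAE tables ought to reconcile.* They differ by design. Under Protocol 7.2.5, a death attributed solely to MDS progression is recorded on the death form and not as an AE.
- *Transplant recipients lose most of their 30 days.* With the recommended washout the loss is about 2 to 3 days.
- *Date imputation reduces the window to nothing.* SAP 6.1.1 moves a new-therapy date with a missing day to the last dose date plus one when the months match. That would give d = 1 if the same date drove the TEAE cut, but the SAP does not say that it does.

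The listings also keep every excluded event visible. A listing is not a comparison between arms, however, so that answers only part of the point.

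**Conclusion.** The point holds as a limited gap between what is collected and what is compared. For new therapy starting on Day d of 1 to 30, 31 - d days of collected AEs fall outside every TEAE table by arm, and their term, grade and relatedness are only listed. This follows from the text and needs no assumption. SAP 7.1.7.2 does not state its own window; I read it as TEAE-based because Protocol 8.6.2 sends other events to listings.

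The practical size is unknown. Under the illustrative switching rates above, roughly 3% to 31% of the 30-day post-dose observation drops out, but only about 0.4% to 4.7% of observation over six cycles plus 30 days. Those figures rest on assumed rates and uniform timing. A difference between arms is plausible because switching depends on response, but nothing in the documents shows its direction or size.

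A reader might infer that the SAP departs from the protocol or that the TEAE definition is wrong. Neither follows. The case is for an inexpensive addition, not a correction.

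**What to change.** Keep the TEAE definition in Protocol 8.6 and SAP 7.1.5.1/7.1.5.2 as primary. Add to SAP 7.1.6 and 7.1.7 a supplementary by-arm set covering:

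- all AEs;
- AEs of Grade 3 or higher;
- SAEs;
- AEs leading to death;
- AEs of special interest.

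The window for this set would be onset from the first dose through 30 days after the last dose irrespective of new anticancer therapy, plus Days 31 to 70 after the last dose and before new therapy including SCT. Flag each AE that starts on or after new therapy and show flagged and unflagged counts. State in one line how partial new-therapy dates are handled for the flag.

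The cost is one derived flag and a few tables from data already collected. The primary definition is unchanged, so Protocol 8.6 need not be amended. SAP section 1 has the plan finalized before data finalization for the second interim analysis, and the addition can be made then. The downside is that some added events will be due to the new therapy, which the flag makes visible.
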